VII.E.2 *Describe randomization scheme/assignment including ratio such as 1:1, 2:1 etc.*

Phase 1: No randomization

Phase 2

The parent-child dyad will be randomized at a 1:1 ratio by a program developed in Microsoft Access or Excel.

VII.E.3 *Will any questionnaires, surveys, or written assessments be used to obtain data directly from subjects in this study?*

Yes

VII.E.4 *List all questionnaires, surveys, written assessments and ATTACH each one to the application. (NOTE: You are NOT prohibited from attaching copyrighted materials to this application)*

Phase 1

Two focus group questionnaires have been developed: a questionnaire for parents of injured children and a questionnaire for staff who serve these injured children. The questions for the parent interview will be equivalent to the parent focus group questions. The questions for provider key informant interviews will equivalent to those of the provider focus group. At each focus group, one study staff member will ask the questions and a second person will take notes on the answers from the participants. In the telephone interview, notes will be taken by the research staff member completing the telephone interview

Phase 2

The parent and child will be asked to answer 4 questionnaires each over the course of the study: one during hospitalization, one at 6-weeks, one at 3-months and one at 6-months post hospitalization. The 6-week, 3-month and 6-month questionnaires will be the same questionnaire.

Both parent and child will complete the baseline questionnaire and follow-up questionnaire three times.

The parent and the child questionnaires will contain the following validated questionnaires: Strengths and Difficulties Questionnaire; the Pediatric Quality of Life Inventory; CESD; Foa PTSD; Multidimensional scale of perceived social support; open family communication; and how I cope under pressure.

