If an online or mailed questionnaire is not returned within 7 days the research team will attempt to contact the dyad by phone 12 times (for each follow-up period) to remind them to complete the questionnaire or to make arrangements for the questionnaire to be completed at an already scheduled follow-up appointment at the hospital. For 6-week questionnaire, they will be contacted 12 times up to 6 weeks following their eligibility to complete that questionnaire. For 3-month questionnaire, they will be contacted 12 times up to 3 months following their eligibility to complete that questionnaire. For 6-month questionnaire they will be contacted 12 times up to 6 months following their eligibility to complete that questionnaire. After a month of no response for any survey timepoint, we will resend the package or online link. If a dyad does not complete the 6-week questionnaire, they will still be asked to complete the 3-month and 6-month questionnaires.

The research team will complete the medical record abstraction within 12 months of receiving the medical record consent. The data collected from the medical record includes measures of injury severity, the type of injury the child sustained, external cause of injury, length of stay, diagnostic procedures, Glasgow Coma Scale measures, comorbidities, and initial vital signs and all discharge codes.

VII.E.7 *Will you attempt to recontact subjects who are lost to follow-up?*

No - those lost to followup will not be recontacted

VII.E.9 *Will subjects be provided any compensation for participating in this study?*

Yes

VII.E.10 *Cash*

No

VII.E.11 *Gift Card*

No

VII.E.12 *Check*

Yes

VII.E.13 *Who will be providing the research compensation check to the subject?*

Accounting Services directly via the e-Voucher system

VII.E.16 *Other*

Yes

VII.E.17 *Describe:*

Phase 1: A light meal will be provided to all focus groups. For the parent focus groups, on-site child care will also be provided.

Phase 2: None

VII.E.18 *If you plan to compensate subjects using cash, checks or cash equivalent does your unit have a [Cash Handling Procedure](#) in place that has been approved by Accounting Services?*

Yes

VII.E.19 *Describe the compensation plan including*

- *Compensation amount and type per visit*
- *Total compensation*
- *Pro-rating for early withdrawal from study*

Phase 1

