The focus group data and key informant interviews will be analyzed using content analysis and identification of themes. Focus group and interview data will also be used to incorporate changes into the LPC for Injured Kids program.

Phase 2

If we achieve randomization, we will compare the differences in distributions between intervention and control groups using simple chi-square tests for categorical outcomes (low, medium, high levels of coing; being symptomatic for PTSD, Depression, etc.) and t-tests or Wilcoxon rank-sum tests for continuous variables depending on their normality (e.g. scores for PTSD, depression, social support).

If we do not achieve randomization (i.e. distribution of demographics are not balanced across intervention and control arms), we will also adjust for confounding using Generalized Linear Models and appropriate link functions (logit for binary outcomes, linear for continuous outcomes).

XI.2 *Provide the rationale or power analysis to support the number of subjects proposed to complete this study.***Phase 1**

The research team needs each final focus group to contain at least 6 parents or providers to get an adequate response to the focus group questions. The focus group will have potentially unpredictable schedule, either due to children in the home (parents) or heavy work load (providers) therefore we are recruiting 10 members per focus group to ensure we have at least 6 attending each focus group.

Phase 2

We conducted sample size based on testing a moderate effect size of 0.5 standard deviation comparing Trauma Education vs Link. With an alpha of 0.05, a sample size of 134 parent-child dyads in each of the arms (n=268) has 100% power to examine comparisons. We will oversample by 12% for a total n = 300.

XII. Future Research

XII.1 *Do you wish to keep any information about subjects involved with this research project so that members of the current research team may contact them in the future for your own research projects?*

No

XII.2 *Do you wish to keep any information about subjects involved with this research project so that [other researchers](#) may contact them for future research?*

No

XII.4 *Does this project involve storing any data, tissues or specimens for future research?*

No

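### XI.1 applies one-value-per-person tests to scales collected at four waves, so each wave's comparison uses only the forms returned at that wave and ignores the other answers

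*Protocol*

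**What the plan says.** Protocol VII.E.4 has parent and child each complete four questionnaires: "one during hospitalization, one at 6-weeks, one at 3-months and one at 6-months post hospitalization". It adds: "The 6-week, 3-month and 6-month questionnaires will be the same questionnaire". The item list there shows that the main scales (PTSD, depression, coping, social support, family communication, quality of life, strengths and difficulties) are also on the baseline form.

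VII.E.6 expects gaps: "If a dyad does not complete the 6-week questionnaire, they will still be asked to complete the 3-month and 6-month questionnaires". XI.2 sizes the trial for "testing a moderate effect size of 0.5 standard deviation comparing Trauma Education vs Link", with 134 dyads per arm, and then states: "We will oversample by 12% for a total n = 300".

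For Phase 2, XI.1 names "simple chi-square tests for categorical outcomes" and "t-tests or Wilcoxon rank-sum tests for continuous variables depending on their normality". If demographics turn out unbalanced, the team will also "adjust for confounding using Generalized Linear Models and appropriate link functions". XI.1 names no wave, no term for repeated answers from one person and no treatment of missed forms.

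**The concern.** The design is longitudinal with intermittent gaps, but the named analysis is cross-sectional. A t-test, rank-sum test or chi-square test takes one value per person. Run at a given wave, it leaves out anyone who missed that form, even if that person answered the same scale at baseline and at the other follow-ups. The people compared can also change from wave to wave.

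The generalised linear model does not close the gap. It is triggered only by demographic imbalance, is described only as confounder adjustment, and has one outcome per person as written.

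What is at stake is mainly bias. If distressed families return fewer forms, and do so more in one arm, the returned forms give a distorted arm difference. The earlier answers that could correct much of this are already collected.

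**Working it through.** **1. The plan's own power figure.** Inputs from XI.2: 0.5 SD, alpha 0.05 (two-sided assumed), 134 per arm. Power = Φ(0.5 × √(134/2) − 1.96) = Φ(4.093 − 1.96) = Φ(2.133) = 98.35%; the exact t-test gives 98.29%. This is within 2 points of the stated 100%, so the sizing also treats each person as one value. The oversampling is 268 × 1.12 = 300.16, or 150 per arm.

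**2. Power after missed forms.** With m the share missing one form, 150 × (1 − m) per arm remain:

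| m | per arm | power for 0.5 SD |
|---|---|---|
| 12% | 132 | 98.2% |
| 20% | 120 | 97.2% |
| 30% | 105 | 95.2% |

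Lost power at the planned effect is therefore not the issue.

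**3. Bias.** The documents give neither correlations nor a loss mechanism, so these are assumptions: 150 per arm, SD 1, wave correlations 0.6 to 0.7, true benefit 0.30 SD. In one arm only, 6-month loss depends on the 6-week score with a log-odds slope β = 0.8 per SD.

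Hand check: in that arm, the mean earlier score of those who return falls by about β × p, where p is the share missing. The 6-month mean falls by about ρ × β × p. With ρ = 0.6 this is 0.6 × 0.8 × 0.25 = 0.12 SD at 25% missing, and 0.6 × 0.8 × 0.12 = 0.058 SD at 12%. The approximation slightly overstates the shift. Simulation gave:

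| missing at 6 months | t-test, loss in Trauma Education arm | t-test, loss in Link arm | likelihood model using earlier waves | t-test type I error, no true effect |
|---|---|---|---|---|
| about 12% | 0.24 | 0.34 to 0.35 | about 0.30 | 7 to 8% |
| about 25% | 0.18 to 0.20 | 0.40 to 0.42 | 0.30 to 0.31 | 13 to 14% |

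When loss works the same way in both arms, the t-test gives 0.28 to 0.31 and type I error is about 5 to 6%.

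**4. Which repeated-measures model.** Suppose some dyads return no follow-up form at all, depending on baseline distress, in one arm, with about 25% missing. A model on the follow-up waves alone then gives the same biased estimates as the t-test, about 0.20 or 0.40 for a true 0.30. Adding the baseline score as a response restores about 0.30.

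A second setting agrees: true effect 0.50, control-arm forms missed according to baseline score (slope 1.0 per SD), 12% to 30% missing, correlation 0.5 to 0.7. The t-test fell to between 0.43 and 0.30, while the model with baseline stayed at about 0.50. The hand formula gives 0.50 − 0.5 × 1.0 × 0.12 = 0.44 and 0.50 − 0.7 × 1.0 × 0.30 = 0.29 at the two ends.

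If each form is missed according to that day's own unobserved score, a follow-up-only model still gives 0.18 or 0.42 for a true 0.30. No model based on observed scores alone removes that.

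**5. Precision.** Under random loss, using the other follow-up waves cuts the standard error of the 6-month difference by only about 2 to 5%. With baseline in the model, the standard error falls from 0.123 to 0.106 (correlation 0.5) or 0.087 (correlation 0.7) at 12% missing. Nearly all of that comes from baseline: 0.123 × √(1 − 0.5²) = 0.107 and 0.123 × √(1 − 0.7²) = 0.088.

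**The case against.** XI.1 is a short answer on an ethics form. It fixes no timepoint, and a two-sample test at one wave is a legitimate comparison. Repeated-measures modelling and missing-data rules are commonly set out in an SAP, which could add imputation. The bias needs loss that is related to symptoms and differs by arm. The protocol gives both arms the same payments (VII.E.19), the same survey formats and up to 12 reminder calls per wave (VII.E.6), and some programme plus a 6-week call. A 25% loss is about twice the 12% oversample.

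Much of this stands. The bias is conditional, and nothing in the documents shows that loss will differ by arm. What remains is that XI.1 states which tests will be used, and VII.B.11 says that no separate written protocol will be submitted, so a stated method is at issue and not an unstated detail. Differing loss is also possible: participants are not blinded (VII.E.1.a), and the 6-week call is a booster session in one arm and a brief survey in the other (VII.E.6). Oversampling replaces numbers; it does not undo selection.

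Two stronger readings are tempting. A reader might infer that the three follow-up forms would be stacked and tested as if independent; nothing in XI.1 proposes that. A reader might also infer that missed forms leave the trial underpowered; at the planned 0.5 SD, power stays at about 95% with 30% of forms missing.

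**Conclusion.** The point holds in a conditional form. As written, and absent imputation in an SAP not shown, each wave's arm comparison rests on that wave's returned forms alone. Under the stated assumptions, score-related loss in one arm shifts a true 0.30 SD by about 0.05 SD at 12% missing and about 0.11 SD at 25%, in either direction. Loss that works alike in both arms does almost no harm. The documents do not show that the result will be biased, only that the named tests offer no protection if loss differs by arm. The correlations, loss rates and loss mechanism are all assumed. The change is worth making because the data are already collected and the remedy is wording only.

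**What to change.** In XI.1, make the main analysis of each score a linear mixed model for repeated measures. Include the baseline score as one of the repeated responses, with arm means constrained equal at baseline, and add wave, arm by wave, hospital and an unstructured within-person covariance. Use all randomised participants with any baseline or follow-up form, and report the arm difference with its 95% confidence interval at each wave.

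Use corresponding repeated-measures models for the binary outcomes and for three-level coping, reporting the arm contrast on the population scale so that it answers the same question as the chi-square test. Keep the t-test and chi-square as descriptive checks.

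The cost is analysis wording and a slightly more complex model; no new data are needed. The model assumes that missingness is explained by the observed scores and arm, and it does not correct loss driven by the unobserved current score.

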According to the Centers for Disease Control and Prevention, the number one cause of death and morbidity among children ages 1-19 is unintentional injury. Each year, approximately 12,000 children die from unintentional injury causes (1). Of all injury causes, motor vehicle crash leads to the most number of deaths to children in U.S. as passengers, teen drivers and pedestrians. Almost 400,000 injured teen drivers and occupants were seen in emergency departments in the US in 2005 (2). In the U.S., falls lead to the highest number of childhood injury emergency department visits followed by injuries due to being struck by or against an object (1). Fire or burns are also an important cause of injury as the second leading cause of injury death to children between 1 and 19 (1).

Unintentional injuries, particularly severe injuries that impact daily functioning, can have longlasting psychological effects. Prevalence of posttraumatic stress symptoms is estimated at 29% during the first month post-trauma and 13% between 3-6 months post-trauma. (3)

Within 12 months of being hospitalized because of injury, 19-32% of adolescents developed PTSD. (4) A variety of injury experiences can lead to PTSD symptoms including traffic crashes, burns, falls and animal attacks. (5) Adolescents involved in a mass burn incident had significantly more mental problems than community controls one year after the incident (6), and, 12% of schoolchildren exposed to an industrial fire met the criteria for PTSD. (7) Approximately 30% of pediatric pedestrian injury cases have acute stress disorder or PTSD. (8-10) Many cases of psychological trauma are missed in hospital settings and sent home. This proposed project will empower families with skills to identify trauma-induced mental health distress and resources for referral to advanced mental health care.

Our innovative project addresses the need for evidence-based practices to improve the acute care of children post-injury. Psychological First Aid (PFA), analogous to physical first aid (11), “uses interpersonal skills provided by individuals to respond to psychological consequences of [trauma] in their own lives, as well as in the lives of their family, friends, and neighbors (p. 4–5)” (11). Informed by previous research on posttraumatic risk and resilience, PFA provides information, education, comfort and support through human contact in order to accelerate recovery and promotion of mental health (12, 13).

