VII.D.31 *What are the plans for the assent process for children/minors in this study? (You may choose more than one procedure if you have different child populations in your study)*

- Children/minors will sign an assent or consent document -

VII.D.36 *Provide a detailed description and rationale for each of the procedures chosen above and describe the child/minor populations to which they apply in your study.*

Phase 2

All children 10-17.2 years of age will be asked to sign an assent document. We chose to use the assent document for all participants aged 10-17.2 years because the language is simple and easy to understand, especially since the children are undergoing medical procedures in the hospital.

It was discovered on 7/15/2016 that some children who signed the assent document turned 18 at some point during the 9-month follow-up period of the study. For research subjects that were assented as children but turned 18 prior to the end of their involvement in the study, the research team will mail a re-consent instruction letter along with a new consent document to the subject. The consent document will be different than the consent document signed by the parent at initial recruitment. The documents will be mailed to research subjects via U.S. mail and provided a postage paid envelope in which to return the signed consent document to the research team.

VII.D.37 *Does the study include any form of deception (e.g., providing participants with false information, misleading information, or withholding information about certain study procedures)?*

Examples:

- *Procedure includes a cover story that provides a plausible but inaccurate account of the purposes of the research.*
- *Participants will be provided with false information regarding the particular behaviors of interest in the research.*
- *Procedures include a confederate pretending to be another participant in the study.*
- *Participants will be told that the research includes completion of a particular task, when in fact, that task will not be administered.*
- *Study is designed to introduce a new procedure (or task) that participants are not initially told about.*
- *If yes, a waiver of informed consent must be requested under question IV.3.*

No

VII.E. Project Description (E)

VII.E.1 *Will subjects be randomized?*

Yes

VII.E.1.a *Will any subjects be blinded to which study arm they have been assigned?*

No

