The questionnaires listed are contained within the attached documents. Please see the following for where they can be found in both parent and child surveys. Parent Baseline Survey #11 is Foa PTSD (#8 in follow-up surveys) #13 is Multidimensional scale of perceived social support (#2 in follow-up) #14 is CES-D (#3 in follow-up) #16 is How I cope under pressure (#5 in follow-up) #17 is Open family communication (#7 in follow-up) #21 is Quality of Life (#9 in follow-up) #22 is Strengths and Difficulties (#10 in follow-up) Child Baseline Survey #6 is the Pediatric Quality of Life Inventory (#9 in follow-up surveys) #7 is Strengths and Difficulties (#10 in follow-up) #9 is Foa PTSD (#3 in follow-up) #10 is CES-D (#4 in follow-up) #11 is How I cope under pressure (#5 in follow-up) #12 is Multidimensional scale of perceived social support (#7 in follow-up) #13 is Open family communication (#8 in follow-up)

VII.E.5 *Does this project involve creating any audiotapes, videotapes, or photographs?*

Yes

VII.E.6 *Provide a detailed description in sequential order of the study procedures following the consent process - DO NOT cut and paste from the Consent Document.*

Describe study populations separately if they will be participating in different procedures - include CONTROL population if applicable.

DESCRIBE:

- *What subjects will be asked to do/what happens in the study (in sequential order)*
- *The time period over which procedures will occur*
- *The time commitment for the subject for individual visits/procedures*
- *Long-term followup and how it occurs*

Phase 1

Participants will be asked to come to a 60-90 minute focus group session at the University of Iowa and Blank Children's Hospital. During each focus group, participants will be asked questions about their opinions, recommendations and additions to the LPC for Injured Kids materials, and the applicability of the program in a rural Iowa population. Each focus group will be audio recorded to ensure all recommendations, additions or corrections are documented. This audio recording will be done with a hand held audio recorder. Audio transcripts of each focus group will be downloaded into a password protected computer. The expected time to complete the telephone interview is 20-30 minutes and will answer the questions asked of the focus group.

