If a health care provider is unable to attend the focus group but interested in participating in a key informant interview, [name] will complete the interview. The key informant interview questions will be equivalent to those of the provider focus group. These interviews will also be audio recorded, transcribed and downloaded into a password protected computer.

The time commitment will be 60-90 minutes. There will be no follow-up visits.

Participants are free to not respond to any questions they prefer not to answer.

Phase 2

All subjects: Following consent, the research team will collect contact information (address, phone number, e-mail addresses) from the parent-child dyad. The parent-child dyad will then complete their baseline questionnaires. Each questionnaire will take approximately 10 minutes to complete. The questionnaire will measure depressive symptoms, symptoms of post traumatic stress disorder, social support, strengths and weakness, quality of life and family communication. The contact information and baseline questionnaires will be collected with an iPad or by paper form, and entered into electronic databases upon return to the research team space in Westlawn at the UIHC site and the Clinical Trials Coordinators office in the Division of Developmental and Behavioral Sciences at Children's Mercy Hospital and filed in locked filing cabinets. Identifying data will be kept separate from questionnaire data.

Link is our new program of psychological first aid adapted from LPC. After our early formative phase 1 work, we had made some modifications to LPC that were not in agreement with the original developers. In order to translate LPC to a program that was acceptable and appropriate for our population, and also after consultation with UI Legal Counsel, we decided to create Link. Therefore, we would not run into copyright issues. Link has elements similar to that described in the LPC program that we created - including screening for stress and motivational interviewing skills. The large difference in Link is that the three original LPC steps - Listen Protect and Connect are not referenced. However, both programs are based on psychological first aid.

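### Covariate adjustment depends on whether demographics look balanced, chance imbalance is called failed randomization, and the outcomes' own baseline scores go unused

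*Protocol*

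**What the plan says.** Section XI.1 (Phase 2) has two branches. If randomization is considered achieved, categorical outcomes are compared by chi-square and continuous ones by "t-tests or Wilcoxon rank-sum tests for continuous variables depending on their normality (e.g. scores for PTSD, depression, social support"). No covariate is mentioned. The second branch reads: "If we do not achieve randomization (i.e. distribution of demographics are not balanced across intervention and control arms), we will also adjust for confounding". The tool named for that adjustment is the generalized linear model. The section gives no criterion for imbalance, names no covariates, and does not say which result leads when both exist.

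The other relevant places are:

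- **VII.E.2, allocation:** "The parent-child dyad will be randomized at a 1:1 ratio by a program developed in Microsoft Access or Excel".
- **VII.E.4, instruments:** the section opens its list with "The parent and the child questionnaires will contain the following validated questionnaires" and then maps each baseline item to its follow-up item. In the child survey, for example: "9 is Foa PTSD (#3 in follow-up) #10 is CES-D (#4 in follow-up"). The mapping covers 7 instruments for the parent and the same 7 for the child: PTSD, depression, social support, coping, family communication, quality of life, and strengths and difficulties.
- **VII.E.6, baseline content:** "The questionnaire will measure depressive symptoms, symptoms of post traumatic stress disorder, social support, strengths and weakness, quality of life and family communication".
- **VII.E.1.a, blinding:** to the question "Will any subjects be blinded to which study arm they have been assigned" the answer is no.

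**The concern.** Randomization is a procedure. If the program allocates dyads 1:1 as described, randomization has been achieved whatever the baseline table shows. A rule that reads chance imbalance as failure would put a misleading label on a sound trial. It would also let the observed data decide whether an adjusted analysis is done.

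The trigger also looks at the wrong variables. Balance matters for a covariate in proportion to how well it predicts the outcome, and the best candidate is usually the same score at baseline. As written, the trigger is defined by demographics alone. A chance gap in baseline PTSD score would not set it off, and the default tests would leave that gap in the estimate.

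The stake is not the validity of the overall test. It is interval width, a shifted estimate in a minority of trials, and the wrong description of the design.

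**Working it through.** **Inputs from the protocol.** 134 dyads per arm (268), effect 0.5 SD, alpha 0.05, stated power 100% (XI.2); 14 paired scores, 7 parent + 7 child (VII.E.4).

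**Assumptions, because the protocol gives no figure.** Two-sided alpha. Baseline to follow-up correlation r = 0.3, 0.5 or 0.7. k = 3, 6 or 10 independent demographics, each tested at 5%.

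**Stated power.** The two-sided normal approximation gives 98.4% and the noncentral t gives 98.3%. The stated 100% is therefore high by less than 2 points.

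**How often correct randomization would be labelled as failed.** 1 − 0.95^k = 14.3%, 26.5% and 40.1% for k = 3, 6 and 10.

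**Precision.** The standard error of the unadjusted difference is √(2/134) = 0.1222 SD, so the 95% half-width is 1.96 × 0.1222 = 0.239 SD. The formulas for the table are:

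- adjusted half-width: 0.239 × √(1 − r²)
- size of an unadjusted trial with the same precision: 268/(1 − r²)
- change-score half-width: 0.239 × √(2(1 − r))
- shift of the unadjusted estimate when the baseline score differs by 0.239 SD: r × 0.239

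| r | Adjusted half-width (SD) | Equivalent unadjusted dyads | Change-score half-width (SD) | Shift (SD) | Power at 0.5 SD, adjusted | Power at 0.3 SD, adjusted |
|---|---|---|---|---|---|---|
| 0.3 | 0.228 | 295 | 0.283 | 0.072 | 99.0% | 73% |
| 0.5 | 0.207 | 357 | 0.239 | 0.120 | 99.7% | 81% |
| 0.7 | 0.171 | 525 | 0.185 | 0.168 | >99.9% | 93% |

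Unadjusted power is 98.3% at 0.5 SD and 69% at 0.3 SD. The change-score column covers the possibility that the scores in XI.1 mean changes from baseline, which the section does not say. At each r the change-score interval is wider than the adjusted one.

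**How often the rule is silent when it matters.** A gap of at least 0.239 SD (z = 1.96) in a given baseline score, with no demographic flagged, has probability 0.05 × 0.95^k = 4.3%, 3.7% or 3.0% for k = 3, 6 or 10, if the demographics are unrelated to that score. Given a gap of exactly z = 1.96, the type I error of the unadjusted test is 1 − Φ((1.96 − 1.96r)/√(1 − r²)) + Φ((−1.96 − 1.96r)/√(1 − r²)) = 7.9%, 12.9% or 20.5% for r = 0.3, 0.5 or 0.7.

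**Overall error of the conditional rule.** This was simulated with 20,000 trials per setting, 5 demographics of which one correlates 0.3 with the outcome, and r = 0.5. Type I error was 5.1% for the rule, 5.5% if the better of the two results is reported, and 5.1% for always adjusting for the baseline score. Power at 0.3 SD was 68% for the rule and 80% for always adjusting.

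**Binary PTSD.** Section 1.6 gives "Prevalence of posttraumatic stress symptoms is estimated at 29% during the first month post-trauma and 13% between 3-6 months post-trauma". Taking 13% as a planning assumption means about 0.13 × 268 = 35 cases. In 2,000 simulated trials per setting, the half-width of the risk difference was about 7.9 points unadjusted and 7.7, 7.4 or 6.9 points after adjustment at r = 0.3, 0.5 or 0.7.

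**The case against.** The strongest reply is that no inference goes wrong. The unadjusted test is valid, power at the planned effect is already about 98%, and the Phase 2 aim in section 1.5 is exploratory. This stands as a limit on severity. An exploratory aim is nevertheless one of estimation, where interval width counts.

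Second, the protocol says the adjusted model is added, not substituted. That is correct, so the unadjusted result always exists. But whether an adjusted result exists still depends on observed balance, and which of the two leads is not stated.

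Third, the generalized linear model names no covariates, so baseline scores are not excluded, and covariate lists are often left to an analysis plan. That is also true. But the model is run only when demographics look unbalanced. In the other branch the baseline scores are unused, and that is a rule the protocol fixes, not a detail it leaves open.

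Fourth, the correlations could be lower, since baseline is taken in hospital soon after injury and follow-up runs to 6 months. At r = 0.1 or 0.2 the half-width would be 0.238 or 0.235 SD, equivalent to 271 or 279 dyads. The gain then nearly vanishes, but adjustment does no harm.

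Finally, the gains for continuous scores are normal-theory figures, and none was computed against the Wilcoxon test. That caveat stands.

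**Conclusion.** The concern holds and should be fixed, although it does not threaten the validity of the comparison. The protocol equates chance demographic imbalance with failed randomization, lets that decide whether adjustment is done, and leaves 14 available baseline scores out of both the trigger and the default tests.

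For r between 0.3 and 0.7, always adjusting narrows the interval by about 5% to 29% (0.239 to 0.228 or 0.171 SD). It also removes an expected shift of 0.07 to 0.17 SD in the roughly 3% to 4% of trials, per score, where a baseline gap of about 0.24 SD goes unflagged. Power at 0.5 SD hardly changes; at 0.3 SD it rises from 69% to between 73% and 93%. These sizes rest on assumed correlations and assumed 5% balance tests. The faults in the wording and in the trigger do not depend on them.

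**What to change.** Remove both conditions on whether randomization was achieved from XI.1 and state instead:

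> Each continuous score is analysed by a linear model with arm, the baseline value of that score and site, whatever the observed balance; the t or Wilcoxon test is supportive. Each binary outcome that has a baseline score is analysed by a logistic model with arm and that score only, and reported as a marginal risk difference beside the chi-square comparison. Three-level coping and outcomes without a baseline value keep their planned tests. Baseline characteristics are shown by arm and do not choose the model.

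Add a rule for missing baseline values, such as the overall mean across both arms; this does not deal with missing follow-up. State also that the baseline questionnaire is completed before the arm is disclosed. Subjects are not blinded, and VII.E.6 places the questionnaire after consent without saying when randomization occurs. The site term can be dropped without affecting the main point. Which follow-up time the model addresses is a separate choice.

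**Cost.** No new data; only the analysis text and program change.

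- The linear model uses 3 to 4 degrees of freedom out of 268: 1 for baseline and 2 to 3 for site, since VII.A.1 lists three hospitals and VII.A.10 names a fourth.
- The logistic model yields a conditional odds ratio. In simulation with an assumed 0.5 SD shift in an underlying score, the odds ratio moved from about 0.35–0.36 unadjusted to 0.35, 0.32 or 0.25 at r = 0.3, 0.5 or 0.7. The risk difference stayed at about −7.7 to −8.0 points with or without adjustment, which is why the marginal risk difference should be reported.
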